8.1. Progranulin Plasma Samples

Blood samples will be collected for evaluation of levels of PGRN in plasma.

PGRN plasma samples will be collected prior to study drug administration on weeks 1, 2, 5, 9, 13, 17, 21, 25, 29, 33, 37, 41, 45, 49, 53, 61 (24 h also), 73, 85, 97, and 105 or study completion/ET for all participants.

The absolute value, absolute change, and percent change from baseline of plasma PGRN will be presented in data listings by cohort and timepoint for the Full Analysis population. Plasma PGRN concentration data will be summarized by cohort and timepoint for the Full Analysis population using descriptive statistics: number of participants with non-missing data (n), mean, SD, CV, median, minimum, maximum, geometric mean and geometric CV. All plasma PGRN concentration values that are BLQ will be set to $\frac{1}{2}$ the lower limit of quantification (LLOQ) when calculating summary statistics.

Mean (\pm SD) absolute value, absolute change and percent change from baseline in plasma PGRN concentration versus nominal time profiles will be plotted on linear and semilogarithmic scales by cohort for the Full Analysis population. In addition, the absolute value, absolute change and percent change from baseline in plasma PGRN concentration at the individual level versus actual time profiles will be plotted on linear and semilogarithmic scales by cohort for the Full Analysis population.

8.2. Progranulin Cerebrospinal Fluid Samples

CSF samples will be evaluated for levels of PGRN. Cerebrospinal fluid samples will be collected in Part 1 only via lumbar puncture prior to study drug administration (if applicable) at Screening, Week 25, Week 49, and Week 97 (or the Part 1 EOT/EOS Visit) to evaluate PGRN.

The absolute value, absolute change, and percent change from baseline in CSF PGRN will be presented in data listings by cohort and timepoint for the Full Analysis population. CSF PGRN concentration data will be summarized by cohort and timepoint for the Full Analysis population using descriptive statistics: number of participants with non-missing data (n), mean, SD, CV, median, minimum, maximum, geometric mean and geometric CV. All CSF PGRN concentration values that are BLQ will be set to $\frac{1}{2}$ the lower limit of quantification when calculating summary statistics.

Mean (\pm SD) absolute value, absolute change and percent change from baseline in CSF PGRN concentration versus nominal time profiles will be plotted on linear and semilogarithmic scales by cohort for the Full Analysis population. In addition, the absolute value, absolute change and

percent change from baseline in CSF PGRN concentration at the individual level versus actual time profiles will be plotted on linear and semilogarithmic scales by cohort for the Full Analysis population.

9. Exploratory Clinical outcome Assessments

All COAs will be collected at the timepoints identified in [Appendix 14.1](#), [Appendix 14.2](#), [Appendix 14.4](#) and [Appendix 14.5](#). The details of the COA are provided in Protocol Appendix 2.

Summaries of COA data will be provided using the Safety population. All COA data will be listed using the Enrolled population.

All COAs, except where indicated, will be assessed using MMRM methodology. The dependent variable will be the change from baseline to each postbaseline visit assessment. The fixed effect will include cohort, and time point will be the repeated measure. An interaction term for timepoint with cohort will be included. Covariates will not be explored due to small sample size. The MMRM will be constructed using unstructured covariance structure, however if the model will not converge AR(1) could be assessed. Estimates of the Least-squares mean, standard error, and 95% CI will be presented for each cohort and timepoint. The least-square means and 95% CI will be plotted by cohort and timepoint.

9.1. Analysis visit windows

The following analysis visit windows will be used for all COAs analyses:

Study day	Analysis Visit
Less or equal to 1	Baseline
Between 2 and 127	Week 13
Between 128 and 211	Week 25
Between 212 and 295	Week 37
Between 296 and 379	Week 49
Between 380 and 463	Week 61
Between 464 and 547	Week 73
Between 548 and 631	Week 85
Between 632 and 757	Week 97
Between 758 and 925	Week 121
Between 926 and 1093	Week 145
Between 1094 and 1275	Week 169
Greater than or equal to 1276	Week 197

9.2. Clinical Dementia Rating Dementia Staging Instrument plus National Alzheimer's Disease Coordinating Center Frontotemporal Lobar Degeneration Behavior and Language Domains (CDR® plus NACC FTLD)

The CDR® plus NACC FTLD results will be summarized by visit and domain. The Global Scores and individual domains will be summarized using the frequency count and percentage of participants in each result and the actual values and changes from baseline using descriptive statistics. The Sum of Boxes and Global Scores will be summarized for actual values and changes from baseline using descriptive statistics. Mean change from baseline, plus or minus the SD, will also be presented in a plot. Subject level data will be presented in a plot, grouped by cohort.

The Sum of Boxes will be assessed using the MMRM methodology described in [Section 9](#).

9.3. Frontotemporal Dementia Rating Scale (FRS)

The FRS results will be summarized by visit and question. The question results will be summarized using the frequency count and percentage of participants in each response. The FRS Score, FRS Percentage Score, FRS Logit Score, and FRS Severity Category Score will be summarized for actual values and changes from baseline using descriptive statistics. Mean change from baseline, plus or minus the SD, will also be presented in a plot. Subject level data will be presented in a plot, grouped by cohort.

The FRS Score and FRS Percentage Score endpoints will be assessed using MMRM methodology described in [Section 9](#).

9.4. Clinical Global Impression of Severity (CGI-S) and of Improvement (CGI-I)

The CGI-S and CGI-I results will be summarized by visit and question.

The question results will be summarized using the frequency count and percentage of participants in each response. In addition, the numeric score for each result will be summarized for actual values (both CGI-S and CGI-I) and changes from baseline (CGI-S only) using descriptive statistics. Mean (CGI-I), plus or minus the SD, will also be presented in a plot. Subject level data will be presented in a plot, grouped by cohort.

For the purposes of summarization using descriptive statistics and plots, the CGI-S Likert scores will equal character responses as follows: 1=Normal, not at all; 2=Borderline ill; 3=Mildly ill; 4=Moderately ill; 5=Markedly ill; 6=Severely ill; and 7=Among the most extremely ill.

For the purposes of summarization using descriptive statistics, and plots, the CGI-I Likert scores will be anchored to 0 as follows: -3=Very much worse; -2=Much Worse; -1=Minimally worse; 0=No change; 1=Minimally improved; 2=Much improved; 3=Very much improved.

9.5. Color Trails Test (CTT)

The CTT results will be summarized by visit and test. The question results will be summarized using the frequency count and percentage of participants in each response. The duration of the pretest and test will be summarized for actual values and changes from baseline using descriptive statistics. Mean change from baseline, plus or minus the SD, will also be presented in a plot. Subject level data will be presented in a plot, grouped by cohort.

In addition, CTT2 total time - CTT1 total time and CTT2 total time/CTT1 total time will be calculated and summarized.

The duration of test endpoint will be assessed using MMRM methodology described in [Section 9](#).

9.6. Repeatable Battery for the Assessment of Neuropsychological Status (RBANS)

The RBANS results will be summarized by visit, domain, domain index score, and overall index score. The domain and overall index scores will be summarized for actual values and changes from baseline using descriptive statistics. Mean change from baseline, plus or minus the SD, will also be presented in a plot. Subject level data will be presented in a plot, grouped by cohort.

The index score endpoints will be assessed using MMRM methodology described in [Section 9](#).

9.7. Neuropsychiatric Inventory (NPI), [REDACTED] [REDACTED]; Part III), Delis-Kaplan Executive Function System (D-KEFS), and Interpersonal Reactivity Index (IRI)

The NPI, UPDRS, D-KEFS, and IRI were administered on participants enrolled under the original protocol dated 09 Apr 2019. The protocol amendment 1 dated 26 Sep 2019 did not include these assessments. Due to the limited availability of data from this change, the data from these assessments will not be summarized.

9.8. Optional Winterlight Labs Speech Assessments

The optional WLA will be analyzed and reported outside of this SAP.

10. Exploratory Pharmacodynamic Biomarkers

All analyses of exploratory PD biomarker data will be conducted using the Full analysis population.

10.1. Analysis visit windows

The following analysis visit windows will be used for all PD biomarker analyses:

Study day	Analysis Visit
Less or equal to 1	Baseline
Between 2 and 20	Week 2
Between 21 and 43	Week 5
Between 44 and 71	Week 9
Between 72 and 99	Week 13
Between 100 and 127	Week 17
Between 128 and 155	Week 21
Between 156 and 183	Week 25
Between 184 and 211	Week 29
Between 212 and 239	Week 33
Between 240 and 267	Week 37
Between 268 and 295	Week 41
Between 296 and 323	Week 45
Between 324 and 351	Week 49
Between 352 and 393	Week 53
Between 394 and 463	Week 61
Between 464 and 547	Week 73
Between 548 and 631	Week 85
Between 632 and 757	Week 97
Between 758 and 925	Week 121
Between 926 and 1093	Week 145
Between 1094 and 1275	Week 169
Greater than or equal to 1276	Week 197

All PD biomarker analyses will be conducted with one data point per time point and subject. If the measurement is available for the nominal time, its value will be used in the analyses. If the measurement for a nominal time point is missing and measurements for unscheduled visits that fall in the corresponding analysis window are available, the value from the sample collected closest to the nominal time point will be used.

10.2. Exploratory Pharmacodynamic Biomarkers of Neurodegeneration, lysosomal function, and glial activity

Exploratory plasma and CSF PD biomarker samples are collected for evaluation for neurodegeneration (e.g., neurofilament-light chain [NfL]), lysosomal function (e.g., cathepsins), and glial activity (e.g., YKL 40, GFAP), and to potentially evaluate levels of other analytes relevant to disease biology and response to AL001. CSF PD biomarker samples are collected in Part 1 only. The timepoint at which the exploratory PD biomarkers of neurodegeneration are identified in [Appendix 14.1](#), [Appendix 14.2](#), [Appendix 14.4](#) and [Appendix 14.5](#).

For all biomarkers listed in the following table, the absolute value, absolute change, percent change from baseline, and ratio to baseline values for exploratory biomarker parameters will be summarized by visit and cohort using descriptive statistics, including the number of participants, mean, SD, median, min and max. Additionally, for absolute value and ratio to baseline, geometric mean (calculated as $\exp(\text{mean}(\log(\text{absolute value or ratio to baseline})))$) and geometric SD will be summarized. For NfL and GFAP, mean absolute value, mean percent change from baseline values, and geometric mean ratio to baseline plus or minus the SD, will also be plotted versus nominal time points up to Week 49. All biomarker concentration values that are BLQ will be set to $\frac{1}{2}$ of LLOQ when calculating summary statistics. In the case of Vendor not providing LLOQ, such as Cell Carta, data points with results being 0 will be excluded from the analysis.

Exploratory Pharmacodynamic Biomarkers		
C1Qb	[REDACTED]	[REDACTED]
C1Qc	[REDACTED]	[REDACTED]
[REDACTED]	[REDACTED]	[REDACTED]
[REDACTED]	[REDACTED]	YKL40
CTSD	LAMP1	[REDACTED]
[REDACTED]	[REDACTED]	MIF
[REDACTED]	[REDACTED]	[REDACTED]
[REDACTED]	[REDACTED]	GFAP
[REDACTED]	[REDACTED]	[REDACTED]

- For the GFAP analysis, only GFAP data from Quanterix will be used. Data on CSF GFAP initially obtained on the Roche NTK platform will be excluded from the data analysis, as those samples were subsequently re-analyzed on the Quanterix SIMOA platform. At the time of analysis, Roche did not have the capability to analyze plasma samples for GFAP. Since plasma GFAP was analyzed on the Quanterix platform, all GFAP (plasma and CSF) analyses were ultimately conducted on the Quanterix platform in order to maintain consistency between matrices.

- For the biomarker data obtained from Cell Carta, each biomarker was assayed with 7 different peptides. The analysis will only include data from the peptide recommended by the Vendor for each biomarker for analysis. The list of recommended peptides is shown in the following table:

Protein	
C1qB	C1QB_HUMAN_IAFSATR_y4+
C1qC	C1QC_HUMAN_FQSVFTVTR_b2+
CTSD	CATD_HUMAN_VSTLPAITLK_y7+
LAMP1	LAMP1_HUMAN_AFSVNIFK_y6+

- Participants who have completed Study AL001-1 and who enrolled in this study may not have had a CSF collection at screening in this study if the baseline LP was performed in the AL001-1 study within 3 months prior to screening into AL001-2. For those participants, the baseline values for certain CSF biomarkers will be obtained from the data in the AL001-1 study.

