3.3. Description of Study Periods

3.3.1. Part 1 – Treatment Period

Screening

Participants may be consented and screened within 6 weeks prior to Day 1 to determine eligibility.

Treatment Period and Follow-up Period

The planned study treatment period will be a total of 96 weeks. AL001 60 mg/kg will be administered intravenously q4w for a total of 25 doses (up to and including Week 97). Cognitive and functional testing ([Section 6.9](#)), which may include input from the participant and study partner (study partner is described in [Section 4.1.1](#)), will be performed during screening and then every 12 weeks. Imaging will be performed during screening and then every 24 weeks. Lumbar puncture for CSF collection will be performed at screening and then every 24 weeks. Accepted windows for treatment, clinical assessments, and imaging are provided in the Schedules of Assessments ([Table 4](#), [Table 5](#), [Table 6](#), [Table 7](#), [Table 8](#), and [Table 9](#)).

Every effort will be made to follow all enrolled participants for the full 96-week treatment period, irrespective of whether they discontinue study treatment. All participants will be followed for safety at 10 weeks after the last dose of AL001.

Upon completion of the 96-week treatment period, participants who are eligible and provide consent will continue in Part 2 (Optional OLE) of the study (Continuation from Week 97 to Week 101). Participants who do not continue in Part 2 (Optional OLE) will return to the investigational site 10 weeks after their last dose of AL001 for final safety assessments.

In this protocol (Study AL001-2), the term “study drug” refers to AL001.

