6.4. Cerebrospinal Fluid Sampling

Cerebrospinal fluid samples will be collected in Part 1 only via lumbar puncture prior to study drug administration (if applicable) at Screening, Week 25, Week 49, and Week 97 (or the Part 1 EOT/EOS Visit) to evaluate PK, PD, and exploratory PD biomarker measures. The Week 25 lumbar puncture may be adjusted as determined by Alector's review of exploratory PD biomarkers.

Specific information on the collection, processing, storage, and shipment of CSF samples will be provided in a separate manual.

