- ^d Vital signs will be recorded after the participant has been resting for at least 5 minutes in the supine position. On dosing days, vital signs will be recorded prior to infusion (pre-dose) and within 15 minutes after the end of infusion, and once at all other specified time points as indicated. Weight (kg) will be collected at the same visits that vital signs are taken.
- ^e Triplicate 12-lead ECGs will be obtained after the participant has been in the supine position for ≥ 5 minutes. On specified dosing days ECG will be obtained prior to study drug administration and within 60 minutes after the end of infusion, and once at all other specified time points as indicated. Additional ECG monitoring must be performed during the treatment period if clinically indicated.
- ^f Details on timing of vital signs, serum PK samples, triplicate ECGs, serum ADA samples, progranulin plasma samples, exploratory plasma PD biomarker samples, whole blood samples for WBC analysis, and exploratory whole blood PD biomarker samples are provided in [Table 6](#).
- ^g Samples will be collected prior to study drug administration (if applicable).
- ^h If the lumbar puncture is moved to a different visit, the coagulation panel will be moved to the visit immediately preceding the new lumbar puncture visit.
- ⁱ Serology testing will include anti-HCV, anti-HIV, HIV antigen, HBsAg, and total hepatitis B core antibody.
- ^j All women of childbearing potential will have a serum pregnancy test at screening. Urine pregnancy tests will be performed at specified subsequent visits. If a urine pregnancy test is positive, it must be confirmed by a serum pregnancy test.
- ^k Blood serum samples will be collected for determination of ADA prior to study drug administration (if applicable). Additional ADA samples should be collected in participants with signs and symptoms of infusion-related reactions. A sample of blood should be obtained for PK serum and ADA assessment of AL001, and testing should be performed for C-reactive protein, tryptase, and Interleukin 6 (IL-6).
- ^l Cerebrospinal fluid samples will be collected via lumbar puncture prior to study drug administration (if applicable). The timing of lumbar punctures may be adjusted as determined by Alector's review of exploratory PD biomarkers. *GRN* mutation carriers previously treated in Study AL001-1 may not be required to repeat the CSF assessment if it has been performed within 3 months prior to screening.

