In the event that a scheduled assessment is unable to be completed at site, e.g., limited availability/restriction of equipment (e.g., MRI), patient limited time on-site or because a remote visit was completed, the missed assessments may be completed at a future on-site visit as determined and approved by the medical monitor.

The approval of the medical monitor must be obtained prior to completion of these moved assessments.

COVID-19 Reporting

In the event where a study subject is diagnosed with COVID-19 infection, the local health authority recommendations regarding treatment should be followed and the event should be reported as an AE/SAE depending on the severity of infection and diagnosis. Refer to [Section 7](#) of the protocol.

Remote Consent

Where it is allowed by country/site regulations, a remote eConsent will be provided that allows a patient to be remote from the site and participate in the consent process.

Remote Source Document Verification

Remote source document verification will be employed **only** in the following circumstance:

- National law, Regulatory Authorities and IRB/Ethics Committee permit this process and approval is obtained.
- On-site clinical research associate (CRA) visits are not permitted due to continued COVID-19 restrictions.
- There is a need to complete source document verification for the following reasons:
 - Study Data assessment review of critical study milestones (e.g., database lock)
 - Patient safety
 - A significant backlog of data monitoring that could impact data integrity or patient safety.

Prior to commencing remote source document verification, the following documentation must be completed:

- The Site CRA will complete a confidentiality agreement committing to securely destroy any copies of documents received from sites (paper or electronic), nor take any recording during video access.

- Remote source data verification (SDV) will only be completed for subjects who have consented to allow access to their health records remotely.

At Home Study Drug Administration

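### CSF and MRI share analysis windows built on the plasma visits, so a Week 25 or Week 49 lumbar puncture or scan more than 14 days late can lose its visit

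*SAP*

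**What the plan says.** SAP section 2 says that analysis windows apply to the COA and biomarker analyses and are described in the section for each. SAP 9.1 gives the COAs a table built on the COA visits; Week 49 is "Between 296 and 379". SAP 10.1 gives a second table under the words "The following analysis visit windows will be used for all PD biomarker analyses". There Week 49 is "Between 324 and 351" and the next window, Week 53, is "Between 352 and 393". Below that table, a value available at the nominal time is used first. If it is missing, a value from an unscheduled visit inside the window may replace it.

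Protocol 6.4 plans CSF "at Screening, Week 25, Week 49, and Week 97 (or the Part 1 EOT/EOS Visit) to evaluate PK, PD, and exploratory PD biomarker measures". Protocol 3.3.1 says of MRI: "Imaging will be performed during screening and then every 24 weeks". Neither has a window table of its own.

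The protocol foresees deferral. Appendix 3, on COVID-19, leaves lumbar puncture and MRI off its minimum on-site list, names MRI as an example of an assessment that may be missed, and says "the missed assessments may be completed at a future on-site visit as determined and approved by the medical monitor". It sets no upper limit. Protocol Table 4, footnote l, adds: "The timing of lumbar punctures may be adjusted as determined by" the sponsor's review of exploratory biomarkers.

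SAP 10.4 restricts the Week 49 change correlations to participants who have baseline and Week 49 values for both the biomarker and the CDR plus NACC FTLD sum of boxes. SAP sections 2 and 12 stop the cohort-level figures at Week 49.

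**The concern.** A window should reflect the gap between planned assessments of the same kind. The plasma table does that for plasma, and the COA table does it for COAs. CSF and MRI inherit limits set by plasma visits four weeks apart, although their own visits are 24 or 48 weeks apart in Part 1. A valid CSF sample or scan can therefore be assigned to a visit at which nobody else is due one.

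CSF progranulin is a secondary endpoint, the cohorts are small, and the SAP itself reports high attrition. The Week 49 change correlations need a biomarker and a clinical score carrying the same visit label. Two different tables can break that pair even when both measurements were taken on one day.

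**Working it through.** **Inputs.** Planned study days come from the schedules of assessments: Week 21 = 141, Week 25 = 169, Week 29 = 197, Week 45 = 309, Week 49 = 337, Week 53 = 365, Week 57 = 393, Week 61 = 421. Each visit has ±7 days, and MRI a further ±7 days around its treatment visit. The windows are those of SAP 9.1 and 10.1.

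**Reproducing the SAP's limits.** Upper limit = (day of this visit + day of next visit)/2, rounded up; lower limit = previous upper limit + 1. For Week 49 with plasma visits: (309 + 337)/2 = 323, so the window starts on Day 324; (337 + 365)/2 = 351, so it ends on Day 351. Applied to all plasma visits, the rule returns all 22 post-baseline windows in SAP 10.1. Applied to the COA visits, it returns all 12 post-baseline windows in SAP 9.1.

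**Late margin in SAP 10.1.**
- Week 25: 183 − 169 = 14 days.
- Week 49: 351 − 337 = 14 days.
- Week 97: 757 − 673 = 84 days.

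The COA margin at Week 49 is 379 − 337 = 42 days.

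**Where a Week 49 assessment falls if classed by study day.**

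| Case | Days | SAP 10.1 | SAP 9.1 |
|---|---|---|---|
| Lumbar puncture within ±7 | 330–344 | Week 49 | Week 49 |
| Latest permitted MRI (337 + 7 + 7) | 351 | Week 49 | Week 49 |
| Earliest permitted MRI (337 − 7 − 7) | 323 | Week 45 | Week 49 |
| Done at the Week 53 visit (365 ± 7) | 358–372 | Week 53 | Week 49 |
| Done at the Week 57 visit (393 ± 7) | 386–400 | Week 53 or 61 | Week 61 |

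One visit late means 21 to 35 days late, which always exceeds 14. For CSF, Days 352–631 lie in windows with no planned CSF. For MRI, Days 352–463 do; from Day 464 a late scan enters Week 73, where another is already planned. Week 25 behaves alike: done at the Week 29 visit (197 ± 7 = Days 190–204), it falls in the Week 29 window (184–211).

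**Early-termination CSF.** Samples at the end-of-treatment or end-of-study visit can come on any day. One on Day 281, for example, is classed as Week 41, where no CSF is planned.

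**Illustrative precision.** With a constant SD, the standard error varies as 1/√n. The asymptomatic GRN cohort has at most 6 members: Protocol 3.1 admits asymptomatic carriers only from Study AL001-1, and Protocol 1.2.2.1 says that study enrolled 6. Losing one gives √(6/5) = 1.095; losing two gives √(6/4) = 1.225. In a cohort of 20, the cap for each mutation cohort, losing one gives √(20/19) = 1.026.

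**The case against.** The strongest reply is the nominal-time rule. A deferred puncture entered under its Week 49 visit could count as the nominal value and stay there, whatever its study day. That may be so, but the SAP does not say how a deferred assessment is labelled. The fallback does not settle it: a puncture done at the scheduled Week 53 visit is neither unscheduled nor inside the Week 49 window. Protocol Table 4, footnote h, speaks of moving the puncture to another visit, which points towards the new visit's label. The ambiguity stands, and so does the need to resolve it.

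Scope is partly inferred. SAP 10.3 does not invoke the table for MRI; that it applies rests on the word all and on MRI's place in section 10. CSF progranulin is summarised in SAP 8.2, which has no windows, although it is a PD biomarker and enters the correlations in 10.4.

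The routes to deferral are limited. Appendix 3 applies only to pandemic circumstances and needs the medical monitor's prior approval. Footnote l covers lumbar punctures generally, whereas Protocol 6.4 and SAP 7.2 name only the Week 25 puncture as adjustable. These passages must be reconciled.

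A reader might infer that any delay moves a sample, or that moved samples are discarded. Neither is supported. Delays of up to 14 days stay in the window, which covers the protocol's own late tolerance. Displaced values are still listed, CSF progranulin is plotted individually against actual time, and the first correlation analysis in SAP 10.4 is not confined to Week 49.

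**Conclusion.** The mismatch is real at Weeks 25 and 49, and Week 97 is little affected. If values are classed by study day, deferral by one dosing visit always takes a Week 25 or Week 49 lumbar puncture or scan out of its window. A displaced Week 49 value leaves the Week 49 summary, the cohort-level figures and the Week 49 change correlations. A displaced Week 25 value leaves the Week 25 summary and becomes an isolated Week 29 entry. A COA from Day 365 still counts as Week 49, so its pair is broken.

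This rests on three assumptions: that study day rather than recorded visit decides the label, that the table governs MRI and CSF progranulin, and that some assessments were deferred by more than 14 days. The documents give no count of deferrals, so the increases of about 10% and 22% in the standard error show scale only. The analyses are descriptive, with no formal testing. This is a cheap improvement in clarity and in use of the data; it does not threaten the trial's conclusions.

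**What to change.** Give CSF and MRI their own windows, using the limits SAP 9.1 already sets for the same visits:

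- CSF and MRI: Week 25 = Days 128–211, Week 49 = 296–379, Week 97 = 632–757.
- MRI also: Week 73 = 464–547, Week 145 = 926–1093, Week 197 = 1276 onward.

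Use the value closest to the target day. Let a deferred assessment keep its intended visit only within these limits. List values outside them, including early-termination CSF, without summarising them by visit. State explicitly that these windows cover CSF progranulin and MRI.

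These limits keep a one-visit deferral (Days 358–372) at Week 49 but not a two-visit deferral (Days 386–400). That is deliberate. Applying the midpoint rule to the CSF visits alone would give Week 49 = Days 254–505, which is 252 days wide. CSF from Day 500 could then be paired with a clinical score from no later than Day 379, at least 121 days earlier. With shared limits the gap is at most 379 − 296 = 83 days.

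The cost is one short table before database lock and no new data. The price is timing spread within a visit: 41 days early to 42 days late at Weeks 25, 49 and 73, and more at later visits (up to 84 days late at Week 97).

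Two schedule conflicts should be reconciled at the same time: whether only the Week 25 puncture may be moved, and whether lumbar puncture is every 24 weeks (Protocol 3.3.1, which would include Week 73) or as listed in Protocol 6.4, which omits Week 73.
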